6.1.2. Systemic Events

6.1.2.1. Primary Analysis

Endpoints: Proportions of subjects reporting prompted systemic events (fever, decreased appetite, irritability, and drowsiness/increased sleep) within 7 days of each dose

- Analysis time points: Within 7 Days Dose 1; Within 7 Days Dose 2; Within 7 Days Dose 3; Within 7 Days Dose 4; Within 7 Days Supplemental Dose
- Analysis population: Dose 1 to Dose 3 safety population for Doses 1 to 3, Dose 4 safety population for Dose 4, Supplemental dose safety population for supplemental Dose
- Analysis methodology: Descriptive statistics
- Supporting objective: Primary Objective

Reporting results:

The percentage (%) and the numerator (n) and the denominator (N) used in the percentage calculation, and corresponding 95% Clopper-Pearson CI will be presented for each vaccine group at each time points.

6.1.3. Adverse Events

6.1.3.1. Primary Analysis

Endpoint: Proportions of subjects reporting AEs from Dose 1 to 1 month following Dose 3, from Dose 4 to 1 month following Dose 4, and from Supplemental Dose to 1 month following Supplemental Dose

- Analysis time points: Dose 1 to 1 month after Dose 3, and from Dose 4 to 1 month after Dose 4/Supplemental Dose
- Analysis population: Dose 1 to Dose 3 safety population, Dose 4 safety population, Supplemental dose safety population for supplemental Dose
- Analysis methodology: Descriptive statistics
- Supporting objective: Primary Objective

Reporting results:

The percentage (%), number of subjects and the denominator (N) used in the percentage calculation, and corresponding 95% Clopper-Pearson CI will be presented for each vaccine group.

Figures: None

6.1.4. Serious Adverse Events and Newly Diagnosed Chronic Medical Conditions

6.1.4.1. Primary Analysis

Endpoint: Proportions of subjects reporting SAEs and NDCMCs from Dose 1 to 6 months following Dose 4/Supplemental Dose

- Analysis time points: Dose 1 to 6 months after Dose 4/Supplemental Dose
- Analysis population: Overall safety analysis population
- Analysis methodology: Descriptive statistics
- Supporting objective: Primary Objective

Reporting results:

The percentage (%), number of subjects and the denominator (N) used in the percentage calculation, and corresponding 95% Clopper-Pearson CI will be presented for each vaccine group.

Figures: None

6.2. Secondary Endpoints

The ordering of the pneumococcal serotypes in summaries will be as follows:

• c7vPnC serotypes: 8, 10A, 11A, 12F, 15B, 22F, 33F.

6.2.1. Pneumococcal serotype-specific immunoglobulin G (IgG) concentrations of the c7vPnC serotypes 1 month after Dose 3

Endpoint: Pneumococcal serotype-specific IgG concentrations of the c7vPnC serotypes 1 month after Dose 3

- Time points: 1 month after Dose 3
- Analysis population: Dose 3 evaluable immunogenicity, CCI
- Analysis methodology: Descriptive statistics
- Supporting objective: Secondary Objective

Reporting results:

IgG GMCs with their associated 95% CIs will be summarized separately at 1 month after Dose 3 for each of the 7 pneumococcal serotypes by each vaccine group.

The percentage (%) and the number of subjects with serotype-specific IgG concentrations ≥ reference concentrations (n) and the denominator (N) used in the percentage calculation, and corresponding 95% Clopper-Pearson CI will be presented for each vaccine group 1 month after Dose 3.

6.2.2. Pneumococcal serotype-specific immunoglobulin G (IgG) concentrations of the c7vPnC serotypes 1 month after Dose 4

Endpoint: Pneumococcal serotype-specific IgG concentrations of the c7vPnC serotypes 1 month after Dose 4

- Time points: 1 month after Dose 4
- Analysis population: Dose 4 evaluable immunogenicity, CCl
- Analysis methodology: Descriptive statistics
- Supporting objective: Secondary Objective

Reporting results:

IgG GMCs with their associated 95% CIs will be summarized separately at 1 month after Dose 4 for each of the 7 pneumococcal serotypes by each vaccine group.

6.5. Baseline and Other Summaries and Analyses

6.5.1. Study Conduct and Subject Disposition

6.5.1.1. Subject Disposition

Disposition of subjects relative to Dose 1 to 1 month after Dose 3 will be summarized for all subjects as follows: The number of consented subjects and the number and percentage of randomized subjects who are randomized, receive each vaccination (Dose 1, Dose 2, Dose 3), complete from Dose 1 to the visit 1 month after Dose 3, withdraw between Dose 1 to the visit 1 month after Dose 3 and the specific reasons for withdrawal (LAR request, lost to follow-up, failed to return, adverse event, protocol violation, other) will be summarized by vaccine group (according to randomized group assignment). A similar summarization of disposition relative to Dose 4/Supplemental Dose will also be prepared, including the number and percentage of randomized subjects who completed through 1 month after Dose 3, withdrew after 1 month after Dose 3 but prior to Dose 4 by reason, received Dose 4, and withdrew after Dose 4 but before the visit 1 month after Dose 4 by reason. For Group 3, disposition will also include those receiving the Supplemental Dose and those who withdrew after the Supplemental Dose but before the visit 1 month after the Supplemental Dose.

The number of consented subjects and the number and percentage of randomized subjects who are randomized, vaccinated, completed, and withdrawn through 1 month after Dose 3 will be presented for each vaccine group (according to randomized group assignment) and overall.

The above information will also be summarized for the time period from 1 month after Dose 3 through 6 months after Dose 4 (Group 1 and Group 2)/Supplemental Dose (Group 3).

6.5.1.2. Demographic Characteristics

Demographic characteristics will be summarized for the overall safety population, by vaccine group and overall.

6.5.1.3. Medical History

Each reported medical history term will be mapped to a system organ class and preferred term according to MedDRA. The number and percentage of subjects with an assigned vaccine having at least one diagnosis, overall and at each system organ class and preferred term level, will be summarized by vaccine group and overall for the overall safety population.

6.5.1.4. Physical Examination

Significant physical examination findings will be recorded on Medical History or AE pages, as relevant, and reporting done under those endpoints for the overall safety population.

6.5.1.5. Blood Samples for Assay

The number and percentage of randomized subjects providing blood samples within and outside of protocol pre-specified time frames will be tabulated separately for 1 month after Dose 3, before and 1 month after Dose 4, and before and after the Supplemental Dose.

6.5.2. Study Vaccination Exposure

6.5.2.1. Vaccination Timing and Administration

The number and percentage of subjects randomized and receiving each vaccine (c7vPnC and/or Prevnar 13) within the protocol-specified time frame, as well as before and after the specified time frame, will be tabulated for each vaccine group and overall for all randomized subjects. The denominator for the percentages is the total number of subjects in the given vaccine group or overall. In addition, the relation of randomized vaccine to actual vaccine received will be presented as a cross tabulation of the actual vaccine received versus the randomized vaccine

6.5.3. Prior/Concomitant Vaccination and Concomitant Medications Used to Treat SAEs and NDCMCs

Each prior/concomitant vaccine will be summarized according to the Anatomic Therapeutic Chemical (ATC) 4th level classification. The number and percentage of randomized subjects receiving each vaccine (including DTaP-IPV-HebB [Pediarix, supplied to study sites, containing diphtheria, tetanus, acellular pertussis, inactivated poliovirus, and hepatitis B antigens], rotavirus, Hib, MMR, varicella, influenza, others) will be tabulated according to assigned vaccine regimen. Summarization will be done separately for before Dose 1, between Dose 1 and 1 month after Dose 3, between 1 month after Dose 3 and Dose 4, and between Dose 4 and 1 month after Dose 4/Supplemental Dose. The Dose 1 to Dose 3 safety population will be used for first three tables while the Dose 4 safety population will be used for the last one.

Concomitant medications used to treat SAEs and NDCMCs will be summarized for the time points Dose 1 to 6 months after Dose 4 (safety population), and for the separate time points Dose 1 through 1 month after Dose 3 (Dose 1 to Dose 3 safety population), from 1 month after Dose 3 to Dose 4 (Dose 1 to Dose 3 safety population), Dose 4 to 1 month after Dose 4/Supplemental Dose (Dose 4 safety population), and from 1 month after Dose 4 to 6 months after Dose 4/Supplemental Dose (After Dose 4 safety population).

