5.7.4. Recording Prior and Concomitant Treatments

The name and date of administration for all vaccinations should be collected from the time of signing of the informed consent document to 1 month after Dose 4/Supplemental Dose and will be recorded in the CRF. At Visit 1, information on prior vaccinations will also be recorded in the CRF.

Concomitant medications used to treat an NDCMC or SAE should be collected from the signing of informed consent through 6 months after Dose 4/Supplemental Dose (telephone contact) and will be recorded in the CRF.

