- Determine whether any SAEs or NDCMCs have occurred since the previous visit and follow up on any previously reported events to determine the outcome (ie, record stop dates or confirm if they are still continuing) and record as described in Section 8, and record concomitant medications used to treat SAEs and NDCMCs.
- Measure and record the subject's rectal temperature (°F/°C).
- Collect a blood sample of approximately 5 mL for immunogenicity prior to vaccination (a topical anesthetic is permitted).
- Administer a single 0.5-mL injection of Prevnar 13 into the left anterolateral thigh.
- Administer permitted vaccines (to be administered into a limb other than the site of Prevnar 13 injection).

- Site staff will observe the subject for at least 30 minutes after vaccination for any acute reactions. Record any AEs on the CRF and on an SAE form as applicable. Record concomitant medications used to treat SAEs and NDCMCs.
- Issue the subject's legally acceptable representative an e-diary (if device needed). Provide and review instructions on use and completion of the e-diary. Ask the subject's legally acceptable representative to complete the e-diary from Day 1 to Day 7, with Day 1 being the day of vaccination. Provide thermometer or measuring device if needed.
- Remind the subject's legally acceptable representative to contact the investigator or investigator site staff as soon as possible if any significant illness or medical event (eg, emergency room visit or hospitalization) occurs.

- Remind the subject's legally acceptable representative that use of prophylactic antipyretic/pain medication, while permitted, is not recommended on the day of investigational product administration (before or after vaccination).
- The investigator or an authorized designee completes the CRF and updates the investigational product accountability records.

6.3.6. Group 3 Visit 6 (Follow-up and Administration of the c7vPnC Supplemental Dose: 13-Month Visit, 28 to 42 Days After Dose 4)

- Ensure and document that the subject continues to be eligible for the study (see Section 6.5 for withdrawal information), and none of the temporary delay criteria are met.
- Record vaccines administered since Visit 5 as described in Section 5.7.4.
- Review the subject's e-diary data with the subject's legally acceptable representative; collect stop dates of any e-diary events ongoing on the last day that the e-diary was completed and record stop dates in the CRF.

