4.1. Safety Analysis Population

The **overall safety population** will include all subjects who receive at least 1 dose of c7vPnC (in Groups 1 and 2) or Prevnar 13 (in Group 3) and have safety data reported in the study. Subjects will be reported according to the vaccine actually received. The safety population will be the analysis population for safety and reactogenicity endpoints.

Additional safety populations will be defined as follows:

Dose 1 to Dose 3 Safety Population - Subjects receiving Dose 1 and having safety data between Dose 1 and the visit 1 month after Dose 3.

Dose 4 Safety Population - Subjects receiving Dose 4 and having safety data between Dose 4 and 1 month after Dose 4 for Groups 1 and 2 and having safety data between Dose 4 and Supplemental Dose for Group 3.

Supplemental Dose Safety Population - Subjects receiving Supplemental Dose and having safety data between Supplemental Dose and 1 month after Supplemental Dose.

If a subject's actual vaccine dose deviates from the planned vaccination within a particular safety population (eg, overall or Dose 1 to Dose 3), the subject data will be either analyzed for any by-dose presentation, or data will be presented in listings as appropriate according to the vaccine dose actually received.

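### In SAP 6.5.3, the Group 3 overall SAE/NDCMC medication table ends 28–42 days early, two interval tables overlap, and the last uses an undefined population (minor)

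*SAP*

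**What the plan says.** SAP 6.5.3 sets out the medication tables in one sentence.

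- **Overall table.** The medications "will be summarized for the time points Dose 1 to 6 months after Dose 4 (safety population"). The Supplemental Dose is not mentioned.
- **First and second separate intervals.** Dose 1 through 1 month after Dose 3, then 1 month after Dose 3 to Dose 4. Neither is in question here.
- **Third separate interval.** "Dose 4 to 1 month after Dose 4/Supplemental Dose (Dose 4 safety population").
- **Fourth separate interval.** "from 1 month after Dose 4 to 6 months after Dose 4/Supplemental Dose (After Dose 4 safety population"). The end point mentions the Supplemental Dose and the start point does not.

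Three other places bear on this.

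- Protocol 5.7.4 has these medications collected from consent "through 6 months after Dose 4/Supplemental Dose (telephone contact").
- SAP 6.1.4.1 analyses the SAEs and NDCMCs themselves over "Dose 1 to 6 months after Dose 4/Supplemental Dose", in the overall safety population.
- SAP 4.1 describes the overall safety population and then, under "Additional safety populations will be defined as follows", gives three more: Dose 1 to Dose 3, Dose 4, and Supplemental Dose. For Group 3, membership of the Dose 4 population depends on having safety data between Dose 4 and the Supplemental Dose.

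**The concern.** Groups 1 and 2 finish vaccination at Dose 4, so 1 month and 6 months after Dose 4 are natural landmarks for them. Group 3 has one more injection after Dose 4, and its follow-up is counted from that injection. A time point that names only Dose 4 therefore falls at a different stage of follow-up in Group 3 than in the other arms.

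If SAP 6.5.3 is programmed as written:

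- An SAE or NDCMC in the last weeks of Group 3 follow-up would count in the primary endpoint, while its treatment would be missing from the overall medication table.
- Treatment given in the month after Group 3's only c7vPnC dose would appear in two interval tables.
- The last interval would begin at a c7vPnC dose in Group 3 but a month after one in Groups 1 and 2, so its columns would not describe comparable periods.
- The programmer would have to invent the denominator for the last table.

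**Working it through.** The plan states no figure to reproduce here. The check lays the Group 3 visit windows on a time line in days from Dose 4 and compares the intervals in SAP 6.5.3 with it.

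**Inputs**

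- Supplemental Dose: 28–42 days after Dose 4. This is also the 1-month post-Dose 4 visit (Protocol 6.3.6: "Group 3 Visit 6 (Follow-up and Administration of the c7vPnC Supplemental Dose: 13-Month Visit, 28 to 42 Days After Dose 4").
- 1 month after the Supplemental Dose: 28–42 days later (Protocol 6.3.7).
- 6-month contact in Group 3: 168–196 days after the Supplemental Dose (Protocol 6.3.8).
- Length of 6 months after Dose 4: 168–196 days, from the Group 1 and 2 contact windows (Protocol 6.1.7 and 6.2.11).
- Age at Dose 1 in Group 3: 42–98 days (SAP 4.2). Age at Dose 4: 365–386 days (Protocol 6.3.5).

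**Overall table**

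- End of Group 3 follow-up = 28 + 168 to 42 + 196 = day 196 to day 238.
- End of the table as written = day 168 to day 196.
- For the same 6-month length, the shortfall equals the delay to the Supplemental Dose: 28–42 days.
- Full span = (age at Dose 4 − age at Dose 1) + delay to the Supplemental Dose + final follow-up.
- Smallest share: span = (386 − 42) + 28 + 196 = 568 days, and 28/568 = 4.9%.
- Largest share: span = (365 − 98) + 42 + 168 = 477 days, and 42/477 = 8.8%.

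**Third and fourth separate intervals, Group 3**

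- The third ends at 28 + 28 to 42 + 42 = day 56 to day 84.
- The fourth starts 1 month after Dose 4, which is the Supplemental Dose visit: day 28 to day 42.
- Overlap = time from the Supplemental Dose to its 1-month visit = 28–42 days.
- In Groups 1 and 2 the third interval ends where the fourth begins, so the overlap is 0.
- Length of the fourth interval: 168–196 days in Group 3, against 168 − 42 = 126 to 196 − 28 = 168 days in Groups 1 and 2.
- The fourth interval ends at day 196–238 in Group 3, which is the end of follow-up. The interval tables therefore do not stop early.

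**Mid-window example** (Supplemental Dose at day 35, 1 month = 35 days, 6 months = 182 days)

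- The span from Dose 4 is 35 + 182 = 217 days.
- As written, the third interval is day 0–70 and the fourth is day 35–217. Together they last 70 + 182 = 252 days, which is 35 too many. The overall table stops at day 182, which is 35 too few.
- If the fourth interval starts at day 70, the total is 70 + 147 = 217 days, equal to the span. If the overall table ends 6 months after the Supplemental Dose, its shortfall is 0.

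**Populations**

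- Third interval: it uses the Dose 4 safety population. For Group 3 the membership rule looks only at data up to the Supplemental Dose, but the interval runs a month beyond it. The Supplemental Dose safety population exists but is not used in SAP 6.5.3.
- Fourth interval: the population named is none of the four in SAP 4.1. That section carries no redaction mark.

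**Comparison within the SAP.** SAP 6.5.1.1 gives separate end points for Groups 1 and 2 and for Group 3 when it describes disposition. SAP 6.1.3.1 uses the Supplemental Dose safety population for AEs after that dose. SAP 6.5.3 departs from both.

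**The case against.** The best defence is that this is a drafting slip with little consequence.

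- The fourth interval covers Group 3 to the end of follow-up. **This stands.** A reader might infer that Group 3's last month is never tabulated. The text does not support that, because only the overall table stops early.
- The overlap lies between two separate tables, and nothing in SAP 6.5.3 says the intervals must sum to the overall table. Treatment of a chronic condition could span adjacent intervals in any arm. **This stands in part.** A reader might infer that a medication is counted twice within one table, which does not happen. But ongoing treatment crossing a boundary is different from two intervals sharing 28–42 days in one arm only.
- Successive intervals are naturally read as contiguous, so a programmer would supply the missing reference to the Supplemental Dose. **Plausible, but it does not settle the matter.** The sentence names the Supplemental Dose in some places and not in others, and no contiguous reading supplies the missing population.
- The tables are supportive, SAP 5.1 excludes hypothesis tests and decision rules, and SAP 6.1.4.1 already has the right end point. **This stands.** A reader might infer that the primary SAE/NDCMC result is affected. It is not.
- Moving Group 3's last interval wholly to the Supplemental Dose safety population would exclude infants who had Dose 4 but no Supplemental Dose. Protocol 6.3.8 still seeks contact with everyone who had at least 1 dose of Prevnar 13. **This stands**, and it shapes the fix.

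**Conclusion.** The point holds and is minor. Taken literally, SAP 6.5.3 has four faults, all arising from the Group 3 schedule or from population names:

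1. The overall table omits the last 28–42 days of Group 3 follow-up, about 5%–9% of the span from Dose 1.
2. The third and fourth separate intervals share the 28–42 days after the Supplemental Dose in Group 3 only.
3. The third interval's population is defined for Group 3 on data that stop before the interval ends.
4. The fourth interval's population is not defined.

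Group 3 has about 188 infants, but only those treated for an SAE or NDCMC in the affected windows could change a table. The documents give no expected number of these. No collected period is wholly untabulated, and no primary or secondary analysis changes.

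The figures assume that visits fall within the protocol windows, that 6 months has the same length after either dose, and that no definition of the fourth population sits in redacted SAP text. The table of contents shows a redacted entry after SAP 4.2. It follows the immunogenicity populations, whereas SAP 4.1 is where the extra safety populations are listed.

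**What to change.** Amend SAP 6.5.3 as follows.

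- **(a)** End the overall table at 6 months after Dose 4 for Groups 1 and 2, and 6 months after the Supplemental Dose for Group 3.
- **(b)** Start the last separate interval at 1 month after Dose 4 for Groups 1 and 2, and 1 month after the Supplemental Dose for Group 3. For Group 3 infants who had Dose 4 but no Supplemental Dose, start it at 1 month after Dose 4. State the end point used for these infants as well, since they have no Supplemental Dose date.
- **(c)** Replace the undefined population with a defined one that keeps those infants, such as members of the overall safety population who received Dose 4.
- **(d)** Optionally, split Group 3's third interval at the Supplemental Dose and use the Supplemental Dose safety population for the second part, as SAP 6.1.3.1 does for AEs. This also removes the population mismatch in that interval. If the interval stays whole, a sentence should say which Group 3 infants form its denominator.

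The cost is SAP wording and table programming, plus one more Group 3 column or table if (d) is adopted. No new data are needed.

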6.6. Safety Summaries and Analyses

The safety measures local reactions, systemic events, AEs, SAEs and NDCMCs summaries and analyses are described under the Primary Endpoints (see Section 6.1).

9. APPENDICES

None
